- Virological criterion: persistently positive SARS-CoV-2 PCR \geq 21 days.

Although 21 days may not be a particularly long duration in this type of patient, in this study we will use this time reference to identify patients with persistent infection.

Current COVID-19 treatment guidelines recommend the use of a single agent within few days of symptoms for all the patients with mild disease but with risk factors for progression

to severe disease, including immunocompromised condition. Remdesivir remains the only approved antiviral to treat hospitalized patients with COVID-19 in case of progression to LRTI and, in any case, after 10 days from diagnosis patients are no longer eligible for any treatment. Moreover, specific indications for immunocompromised patients are limited to the use of long-acting monoclonal antibodies as SARS-CoV-2 pre-exposure prophylaxis for individuals who may have an inadequate immune response to COVID-19 vaccination. It should also be specified that there is currently insufficient evidence to guide clinical recommendations for other treatments in immunocompromised patients [7].

However, in clinical practice, it appears clear that such recommendations are not sufficient to guarantee the cure of SARS-CoV-2 infection in immunocompromised patients, in particular in the “long persisters” population. Currently in literature, only case reports or small case series have described the prevalence and the management of patients with persisting infection. These studies show a wide variability of therapeutic approaches ranging from the adoption of repeated or prolonged cycles of remdesivir [8-10] or nirmatrelvir/ritonavir [11], dual antiviral therapy [12-13] and combination therapy with antiviral and monoclonal antibodies [14-16]. These case reports show variable success rates and highlight the need for larger studies focused on immunocompromised patients, to identify the best therapeutic approach in this population.

With this premise, we would like to conduct an observational study on immunocompromised patients, and specifically on haematological patients with B cell malignancies diagnosed with SARS-CoV-2 infection, with the aims of assessing the prevalence of those with persisting COVID-19, associated risk factors and describe the different clinical managements and their related outcomes.

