3.1 Primary objective

The primary objective of this study is to describe the prevalence of SARS-CoV-2 persisting infection and the related risk factors in immunocompromised patients with B cell malignancies or undergoing B cell targeting therapies.

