3.3 Endpoints

The first primary endpoint variable will be the prevalence of persisting SARS-CoV-2 infection among the immunocompromised patients defined as the persistence or the recurrence of symptoms and signs (fever, dyspnea, hypoxemia, changes on chest-X ray or CT scan) and positive SARS-CoV-2 PCR ≥ 21 days after the time 0 (day of the first test positive for SARS-CoV2 infection).

The endpoints for the secondary objectives are:

- Duration of treatment carried out to address the persistent COVID-19 condition and treatment-related adverse effects.
- Duration of viral shedding, defined as the number of days between the first positive test and first negative PCR test.
- Duration of symptoms, defined as the number of days between symptoms onset and the clinical cure.
- Prevalence of imaging alterations, defined as the presence of new ground-glass and/or crazy paving and/or interstitial infiltrates at chest CT scan during the persisting infection (starting from 21 days after the first positive test until viral clearance).
- Re-infection within 120 days, define as new positive test with or without symptoms after viral clearance has been achieved.
- All-cause 120-day mortality.

4. Investigational plan

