4.8 Statistical Analysis Plan

Patients' characteristics will be summarized using absolute frequencies and percentages (categorical variables) and mean±standard deviation or median and interquartile range (scale variables, according to their distribution).

The prevalence of persisting SARS-CoV-2 infection among the immunocompromised patients will be obtained as the ratio of the number of patients with evidence of persisting SARS-CoV-2 infection on the total number of enrolled patients.

As for the analysis of risk factors for persisting COVID, comparisons between COVID-persistent and non-persistent patients will be carried out by means of survival analyses for all outcomes expressed as durations (time-to-event analyses). These outcomes will be compared by estimating Kaplan-Meier curves, calculating log-rank tests and multiple Cox regressions in which COVID persistence will be the main risk factor and including the confounders and effect modifiers listed below.

- Age
- Sex
- Comorbidities (Charlson Comorbidity Index)
- Underlying hematologic disease state
- Chemotherapy treatments performed
- Duration of Hospital stay
- Admissions to intensive care
- Days with central venous catheter
- Bacterial and fungal superinfections
- Vaccination status
- Previous SARS-CoV-2 infections
- Serological status (anti-SARS-CoV-2 antibodies)

Re-infection and imaging alterations rates will be calculated as the ratio of the number of events to the overall number of patients, and the comparison between persisters and non-persisters will be carried out by calculating the corresponding risk ratios. A multiple logistic regression model will assess the relationship between exposure and re-infection (image alteration) net of the potential confounders.

For secondary aims, the secondary endpoints will be described just for the patients with persisting COVID, categorical variables will be reported as number and relative

frequencies, continuous variables will be reported as mean±SD or median and IQR according with their distribution.

5. Administrative procedures and declarations

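### Risk factors for persistence are part of the primary objective, but no planned analysis has persistence as the dependent variable

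*Combined protocol and SAP*

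**What the plan says.** The primary objective (section 3.1) is to "describe the prevalence of SARS-CoV-2 persisting infection and the related risk factors in immunocompromised patients". The background (section 2.1) gives the same aim: "assessing the prevalence of those with persisting COVID-19, associated risk factors and describe the different clinical managements".

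Section 3.3 states one primary endpoint: "The first primary endpoint variable will be the prevalence of persisting SARS-CoV-2 infection among the immunocompromised patients". It calls this the first, and no second one for risk factors follows. Persistence is a composite: "persistence or the recurrence of symptoms and signs (fever, dyspnea, hypoxemia, changes on chest-X ray or CT scan) and positive SARS-CoV-2 PCR" at 21 days or more after the first positive test.

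Section 4.8 computes prevalence as a ratio over all enrolled patients. It then opens the risk-factor analysis: "As for the analysis of risk factors for persisting COVID, comparisons between COVID-persistent and non-persistent patients will be carried out" by survival methods on outcomes expressed as durations. The regression models are "multiple Cox regressions in which COVID persistence will be the main risk factor and including the confounders and effect modifiers listed below". A logistic model relates the exposure to re-infection and to imaging alterations. The rest is descriptive.

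**The concern.** A risk-factor analysis needs the condition as the outcome and the candidate factors as predictors. Here the roles are reversed, so the models answer what persistence leads to, not what leads to persistence. A coefficient for age or serostatus in a model that already contains persistence does not estimate that factor's association with persistence. In the mortality model, for example, it estimates the effect on death that does not pass through persistence.

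Part of the primary objective would thus have no matching estimate. A model improvised later from the covariate list in section 4.8 would also inherit four items that can arise after time 0: hospital stay, intensive care admission, catheter days and superinfections. These could be consequences of persistence reported as its causes.

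**Working it through.** **1. Role of persistence in each planned analysis (section 4.8)**

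| Analysis | Outcome | Role of persistence |
|---|---|---|
| Prevalence ratio | Persistence | Outcome, with no predictors |
| Kaplan-Meier, log-rank, Cox | Durations | Grouping variable or main covariate |
| Risk ratios, logistic | Re-infection, imaging | Exposure |
| Secondary endpoints | Described in persisters only | Restricts the population |

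No row has persistence as outcome together with candidate factors as predictors.

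**2. The plan's own power figure (section 4.4.3)**

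Freedman log-rank: E = (1.96+0.842)² × (1+k·HR)² / [k(1−HR)²], with k = 300/700. For 3% against 7% mortality, HR = ln 0.93 / ln 0.97 = 2.383, so E = 39.1. The event probability is 0.7×0.03 + 0.3×0.07 = 0.042, giving N = 39.1/0.042 = 932 (stated 933). For 4% against 9%, N = 768 (stated 768). The table is sound, but it concerns mortality by persistence status and not risk factors for persistence.

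**3. Can the shedding Cox model stand in?**

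The endpoint is "Duration of viral shedding, defined as the number of days between the first positive test and first negative PCR test", while persistence itself requires a positive PCR at 21 days or more, so the two overlap by definition. The simulation assumes N=1,000, a factor present in 30%, exponential clearance with 30% shedding at 21 days, 15% persistent (shedding plus symptoms) and censoring at day 120. Only the 30% shedding figure and the 1,000 come from section 4.4.3, and the 120 days from section 4.5. The Cox model contains persistence and the factor.

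- No true effect: persistence reads HR 0.33 and the factor 1.00.
- Factor slows clearance (HR 0.75): it reads 0.77, significant in 94% of runs. Without the persistence term, detection is about 98%. A logistic model for persistence detects it in 53–55%.
- Factor acts only through symptoms (symptomatic share of long shedders 44% unexposed, 65% exposed; OR for persistence 1.60): it reads HR 1.14, apparently faster clearance, significant in 48%. The logistic model reads 1.60, significant in 72%.

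These runs show that the models target different quantities. They do not forecast results.

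**4. Is the missing model feasible?**

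Two-proportion formula, two-sided 0.05, unadjusted, OR 1.6, N=1,000: power = Φ[(p1 − p0 − 1.96·s0)/s1], where s0 and s1 are the pooled and unpooled standard errors. Exposure prevalence is assumed, as the documents give none; 15% persistence is also assumed.

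| Exposed | Persistent | p0 | p1 | s0 | s1 | Power |
|---|---|---|---|---|---|---|
| 30% | 30% | 0.2695 | 0.3712 | 0.0316 | 0.0325 | 89% |
| 30% | 15% | 0.1310 | 0.1943 | 0.0246 | 0.0262 | 72% |
| 10% | 30% | 0.2895 | 0.3946 | 0.0483 | 0.0512 | 58% |
| 10% | 15% | 0.1432 | 0.2110 | 0.0376 | 0.0424 | 44% |

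The lower prevalence is shown because the 30% in section 4.4.3 counts shedding alone, whereas section 3.3 also requires symptoms or signs.

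**5. Timing in the mortality model**

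A patient must survive at least 21 days to be classed as persistent. Assume no true effect, 4.2% mortality at constant hazard, 30% persistence and the definition first met evenly over days 21–45. Eventual persistence treated as known from time 0 then reads HR about 0.63–0.65. Time-dependent entry reads 1.00.

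**The case against.** The objective says only that risk factors will be described, so a table by persistence status might be enough. But section 4.8 does not say that characteristics will be tabulated by persistence, and a crude table would give the primary objective less than the adjusted models planned for re-infection and imaging.

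A stronger objection is that the shedding Cox model does carry information on risk factors, and for a factor that slows clearance it detects more than the logistic model (94% against 53–55%). That stands. A reader might infer that the planned models say nothing useful about risk factors, or that the logistic model should displace every clearance analysis. Neither follows. The gap is that the section 3.3 composite is never modelled, and a clearance model without the persistence term is worth keeping in support.

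The simulation inputs are assumed, and the misleading result depends on the chosen symptomatic shares. That also stands; the point rests on the comparison of analyses in step 1, not on the simulation.

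A reader might further infer that the investigators mean to choose a model after seeing the data, because section 5.5 lets the analysis be refined after preliminary results. The documents do not show that intent. The sentence belongs to a publication policy, and section 5.3 provides for amendments during enrolment. Neither section supplies the missing model.

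**Conclusion.** Wrong as written. The paragraph labelled as the risk-factor analysis answers a different question, and nothing elsewhere in the plan fills the gap. This follows from the text and needs no assumption. The consequence is that the study would report a prevalence and no estimate of association with the section 3.3 composite.

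A reader might infer that the study is too small or is collecting the wrong data. The documents do not support that: most of the predictors are already listed, and about 300 events are expected by the plan's own count. Power for OR 1.6 runs from 89% down to 44% over the assumed ranges of exposure and persistence, so common factors are within reach and uncommon ones may not be. The mortality sample-size table reproduces and is not in question.

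**What to change.** 1. **Primary risk-factor model.** Replace the risk-factor sentence in section 4.8 with a pre-specified multivariable logistic regression with persistence (section 3.3 definition, yes/no) as the outcome. Limit predictors to those known at or before time 0: age, sex, Charlson index, haematological disease state, prior chemotherapy, prior B-cell-targeting therapy, vaccination, previous SARS-CoV-2 infection, and serostatus where measured by then. Leave out hospital stay, intensive care admission, catheter days and superinfections. Report adjusted ORs with 95% CI.
2. **One main handling rule.** Keep the section 4.8 denominator: all enrolled patients, with those lacking evidence of persistence counted as non-persistent. Report the numbers who die before day 21 and whose status cannot be determined, with one sensitivity analysis excluding both groups. Do not count deaths before day 21 as persistent, since they cannot meet the definition.
3. **Optional support.** Fit a Cox model for time to viral clearance on the same baseline predictors, without the persistence term.
4. **Secondary objective.** Assign the models with persistence as exposure to section 3.2. For 120-day mortality, enter persistence as a time-dependent covariate from the date its definition is first met. Do not test shedding or symptom duration against persistence, as both are tied to its definition. Reconcile section 3.2, which compares the two groups, with the end of section 4.8, which describes secondary endpoints in persisters only.

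**Cost.** SAP wording, one added regression with a sensitivity run, and recoding of the mortality model; no extra patients. B-cell-targeting therapy is an inclusion criterion but not a listed covariate, so it must come from eligibility or chart data. Serostatus may be missing for some. The date the definition is first met must be derivable. The section 4.4.3 log-rank calculation would match the mortality analysis only approximately. Events may fall below 300, which limits the number of model terms.

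The main handling rule is not free of bias. If 10% of unexposed and 20% of exposed patients are undetermined regardless of outcome (assumed, 30% persistence), a true OR of 1.0 reads (0.24/0.76)/(0.27/0.73) = 0.85, while exclusion reads 1.00. If instead 30% of unexposed and 10% of exposed non-persisters are undetermined, the main rule reads 1.00 and exclusion reads (0.30/0.63)/(0.30/0.49) = 0.78. Hence the sensitivity analysis.

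### The Cox models with persistence as the exposure adjust for hospital stay, ICU admission, catheter days and superinfections without a measurement window, so the adjusted hazard ratio may condition on consequences of persistence

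*Combined protocol and SAP*

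**What the plan says.** Section 4.8 of the combined protocol and SAP compares persistent and non-persistent patients by "survival analyses for all outcomes expressed as durations (time-to-event analyses", using Kaplan-Meier curves, log-rank tests and "multiple Cox regressions in which COVID persistence will be the main risk factor and including the confounders and effect modifiers listed below". Four of the twelve listed covariates are "Duration of Hospital stay", "Admissions to intensive care", "Days with central venous catheter" and "Bacterial and fungal superinfections". None has a window, there or elsewhere. The section does not say which variables are confounders and which are effect modifiers, or whether a total or a direct association is wanted. The logistic models for re-infection and imaging changes are to give results "net of the potential confounders", without a list of their own.

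Three other places bear on timing and outcome:

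- Section 3.3 defines persistence by symptoms or signs plus a positive PCR 21 or more days after time 0, the day of the first positive test. It lists all-cause 120-day mortality as a secondary endpoint.
- Section 4.5 sets follow-up at 120 days from diagnosis.
- Section 4.4.3 bases power on a log-rank comparison of 120-day mortality between the two groups, and section 3.2 promises a comparison. Section 4.8, however, ends by saying that "the secondary endpoints will be described just for the patients with persisting COVID".

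**The concern.** A covariate that accrues after the exposure can lie on the path from exposure to outcome. Persistent infection may lengthen a stay, lead to intensive care, or prolong catheter use and so invite superinfection. Adjusting for these removes part of the association that the model is meant to measure, and can add bias if they share unmeasured causes with the outcome. In a mortality model, total stay and total catheter days have a further fault: death ends both, so the covariate carries information about the outcome.

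At stake is the meaning of the adjusted HR for persistence. Section 2.2 expects the results to inform clinical practice and future interventional studies, and readers will probably take that HR as the effect of persistence.

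**Working it through.** **Timing.** The exposure is first known at day 21. Covariates without a window may accrue until day 120, so up to 120 - 21 = 99 days of stay, catheter use, ICU admission and superinfection can follow classification. The protocol does set a window elsewhere: imaging changes count from day 21 until viral clearance (section 3.3).

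**The plan's own figure.** Section 4.4.3, 3% versus 7% mortality, allocation ratio k = 0.43, Freedman method:

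- HR = ln(0.93)/ln(0.97) = 2.383.
- E = (1.960 + 0.842)² × (1 + 0.43 × 2.383)² / [0.43 × (1 - 2.383)²] = 39.1 (stated 40).
- N = 39.1/0.04203 = 931 (stated 933).

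The figure reproduces. It covers the unadjusted log-rank test only and says nothing about the adjusted model.

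**Whole-course stay in a mortality model.** All inputs are assumed. Simulation with n = 400,000 and true HR 1; 30% persisters; qualifying PCR uniform over days 21-35; 120-day mortality 5% or 8%; hazard constant or with 40% of deaths before day 21. Stay is lognormal (sigma 0.8), median 10 days in non-persisters and 15 or 30 in persisters, entered linearly. Entry is at day 21 with time-dependent persistence, so immortal time plays no part. Ranges are over the eight settings:

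| Model | HR |
|---|---|
| Without stay | 0.96-1.05 |
| Whole stay, death only truncates it | 1.01-1.16 |
| Whole stay, 5% of decedents in hospital until death | 0.93-0.98 |
| Same, 15% | 0.70-0.88 |
| Same, 30% | 0.48-0.77 |

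Repeat runs widen these slightly. The rounded ranges are 1.0-1.2, 0.9-1.0, 0.7-0.9 and 0.5-0.8.

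**Against sampling error.** Deaths expected under section 4.4.3:

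- 700 × 0.03 + 300 × 0.07 = 42
- 700 × 0.04 + 300 × 0.09 = 55
- 700 × 0.05 + 300 × 0.10 = 65

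Assume all persister deaths fall after day 21 and that 17.5% (21/120) or 40% of non-persister deaths fall before it. The extremes after day 21 are then 21 × 0.60 + 21 = 33.6 and 35 × 0.825 + 30 = 58.9, or about 34-59 deaths. With SE = sqrt(1/(d × 0.3 × 0.7)), these give 0.38 and 0.28. The shifts are:

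- 30% case: |ln 0.8|/0.38 = 0.6 to |ln 0.5|/0.28 = 2.4 SE
- 15% case: |ln 0.9|/0.38 = 0.3 to |ln 0.7|/0.28 = 1.3 SE
- 5% case: at most |ln 0.9|/0.28 = 0.4 SE
- Truncation only: at most ln 1.2/0.28 = 0.6 SE

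This SE is unadjusted. With twelve covariates it would be larger, so the multiples are upper bounds.

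**Mediators.** This is a change of estimand, not a bias. Under assumed inputs, adjusting for later ICU admission and superinfection moves the HR from 1.91 to 0.98 with full mediation and from 2.09 to 2.00 with weak mediation.

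**Which windows are safe.** These checks use the same kind of simulation with a true HR of 1. Hospital days before time 0 leave the HR at 0.97-1.01, and inpatient status at time 0 at 0.98-1.01. Stay counted over days 0-21 is not safe: 1.06-1.52 followed from time 0 (truncation), and 0.65-0.84 with entry at day 21 (30% in hospital until death). ICU admission in days 0-21, simulated as a true confounder, gives 1.07-1.23 if omitted and 1.00-1.03 if kept.

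**Linked defect: immortal time.** Suppose persistence is a fixed group and time runs from time 0. Persisters then cannot die before qualifying, at day 28 on average under uniform days 21-35. If a fraction f of deaths falls before then, the apparent HR at true HR 1 is about (1 - f)/(1 + (0.3/0.7) × f).

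- Constant hazard: f = 28/120 = 0.233, HR = 0.767/1.100 = 0.70.
- 40% of deaths before day 21: f = 0.40 + 0.60 × 7/99 = 0.442, HR = 0.558/1.190 = 0.47.

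Simulation agrees, at about 0.7 and 0.5.

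**The case against.** Section 4.8 is silent on timing. A reader might infer that it instructs the analyst to use totals to day 120. It does not: it calls the list confounders and effect modifiers, and values from before time 0 may be genuine confounders, since section 4.4 admits patients already in hospital. That stands, and the point is limited to what the text allows. Even so, a duration of stay with no limit is ordinarily read as the whole stay, and the label does not date it.

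A reader might also infer that a Cox model for mortality is planned. No section states one. Section 4.4.3 powers a log-rank test, and the last paragraph of section 4.8 confines the secondary endpoints to description in persisters. If that sentence governs, the mortality figures above do not apply. Sections 3.2 and 4.4.3 point the other way. The lack of windows affects any Cox model fitted with this list, but its size was not worked out for shedding, symptom or treatment duration.

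The 0.5-0.8 range should not be read as the expected bias. It needs 30% of decedents to be in hospital continuously from time 0 to death, in a cohort that includes outpatients. At 5% the two mechanisms nearly cancel.

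Finally, a direct effect may be what is wanted. No section says so, and stay and catheter days would still be unsuitable in a mortality model because death ends them.

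**Conclusion.** The point holds in limited form and should be fixed. Confidence is high that the windows are absent and that post-exposure values are permitted. It is moderate that the distortion would be material.

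If whole-course values are entered, the adjusted HR no longer estimates the total association of persistence with the outcome. Size and sign cannot be derived from the documents. The simulated HRs, from about 1.2 down to 0.5 when the truth is 1, rest on assumed inputs and on a mortality model that is inferred. The fraction of decedents in hospital until death largely determines where in that range the result falls.

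A reader might infer that the study's main results are undermined, or that all four covariates should be dropped. Neither follows. Prevalence, Kaplan-Meier curves and log-rank tests do not use the covariate list, and early or pre-infection values can be legitimate adjustments.

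**What to change.** First reconcile sections 3.2, 4.4.3 and 4.8 on whether 120-day mortality is compared between groups by Cox regression.

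**Covariates (section 4.8).** State that:

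- the target is the total association of persistence with the outcome;
- the main model adjusts only for covariates measured at or before time 0;
- hospital and catheter days are limited to before time 0, or replaced by inpatient and catheter status at time 0;
- ICU admission and superinfection with onset in days 0-21 may be added as earlier severity, with the HR reported with and without them;
- later values are reported by group or in a labelled exploratory analysis.

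Apply the same windows to chemotherapy and serostatus, and to the logistic models if they use this list.

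**Immortal time (separate change).** Start risk time at day 21, with persistence as a time-dependent variable and a landmark analysis as sensitivity. State that the power in section 4.4.3 applies to the unadjusted log-rank test from diagnosis and must be restated for day-21 survivors (about 34-59 deaths).

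**Cost.** SAP wording, plus a few dates: qualifying PCR, ICU admission, superinfection onset, and inpatient and catheter status at time 0. The documents do not show whether the eCRF records these. Deaths before day 21 (about 4-14 of the 42-65, under the assumptions above) are reported separately and do not inform the HR. The main model gives no HR adjusted for later severity.

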4.4 Study population

All immunocompromised adults (≥ 18 years) with a new SARS-CoV-2 infection assessed during the study period, hospitalized or followed as outpatients in the Haematological Units of the participating centers, will be screened for inclusion.

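### No model adjusts for COVID-19 severity at diagnosis, so the persister versus non-persister mortality comparison may partly reflect initial severity; the remedy must go together with correct timing of the exposure

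*Combined protocol and SAP*

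**What the plan says.** Section 3.3 defines a persister by "the persistence or the recurrence of symptoms and signs (fever, dyspnea, hypoxemia, changes on chest-X ray or CT scan) and positive SARS-CoV-2 PCR ≥ 21", counted in days from time 0, which is the day of the first positive test. Section 4.8 recognises only persistent and non-persistent patients, so someone still PCR-positive at that point without symptoms or signs counts as non-persistent.

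Section 4.4 screens patients "hospitalized or followed as outpatients in the Haematological Units of the participating centers", and section 4.4.2 lists no exclusions. The cohort therefore spans a wide range of illness at diagnosis.

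For time-to-event outcomes, section 4.8 plans Kaplan-Meier curves, log-rank tests and "multiple Cox regressions in which COVID persistence will be the main risk factor and including the confounders and effect modifiers listed below". The list has 12 items. Those closest to COVID-19 severity are "Duration of Hospital stay", "Admissions to intensive care" and bacterial and fungal superinfections; none is tied to time 0. The logistic models have no list of their own: "A multiple logistic regression model will assess the relationship between exposure and re-infection (image alteration) net of the potential confounders".

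The mortality endpoint is "All-cause 120-day mortality". Section 4.4.3 bases the sample size on a log-rank test of it, and no stratification is planned.

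**The concern.** Hypoxemia or lung changes present at diagnosis may simply continue to day 21 and so help a patient meet the persistence definition. They also plausibly raise the risk of death. A factor that influences both exposure status and outcome is a confounder, and the plan's own list omits it.

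The three severity-like items do not fill the gap. A long stay, an ICU admission or a superinfection can occur after persistence has begun and may lie on the path from persistence to death. Adjusting for them is not adjusting for severity at baseline.

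At stake is the reading of the mortality comparison, the only one with a power calculation. A difference between the groups could be put down to persistence when part of it was present on the day of diagnosis.

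**Working it through.** **1. The plan's own figure.** Freedman's formula is E = (z₁₋α/₂ + z₁₋β)² (1 + k·HR)² / [k(1 − HR)²], with k = 0.43 and N = E / Pr_E. For survival of 0.97 against 0.93:
- HR = ln 0.93 / ln 0.97 = 2.383
- E = 7.849 × (1 + 0.43 × 2.383)² / (0.43 × 1.383²) = 39.1
- Pr_E = 1 − (0.97 + 0.43 × 0.93)/1.43 = 0.04203
- N = 931.3, which is 933 once group sizes are rounded up, as the table states

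All 17 complete rows reproduce. The power arithmetic is sound; the question is what the hazard ratio measures.

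**2. Inputs for the illustration.**
- From the documents: 700 and 300 patients, 120 days, two-sided 5%.
- Assumed: 4% overall mortality, constant hazard, no effect of persistence within severity strata, lung involvement at time 0 in a share p_P of persisters and p_N of non-persisters, and mortality multiplied by R when it is present.

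**3. Apparent mortality ratio from severity alone.** Ratio = [1 + p_P(R − 1)] / [1 + p_N(R − 1)].

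| p_P vs p_N | R | Ratio |
|---|---|---|
| 50% vs 20% | 2 | 1.50/1.20 = 1.25 |
| 50% vs 20% | 4 | 2.50/1.60 = 1.56 |
| 50% vs 20% | 5 | 3.00/1.80 = 1.67 |
| 40% vs 25% | 4 | 2.20/1.75 = 1.26 |

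**4. Analysis from time 0 with persistence as a fixed group.** Nobody who dies before day 21 can be a persister. With a constant hazard, 21/120 = 17.5% of deaths are that early. Take 50% vs 20% and R = 4:
- Overall share with lung involvement: 0.3 × 0.50 + 0.7 × 0.20 = 0.29.
- Mortality without lung involvement: 0.04 / (1 + 0.29 × 3) = 0.0214.
- Deaths among the 300: 300 × 0.0214 × 2.5 = 16.0. Deaths among the 700: 700 × 0.0214 × 1.6 = 24.0.
- Early deaths moved to the comparator: 0.175 × 16.0 = 2.8.
- Ratio: (13.2/297.2) / (26.8/702.8) = 0.0445/0.0381 = 1.17, down from 1.56.

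Simulation with this rule, for R = 2, 4 and 5, gives ratios of about 0.96, 1.15 and 1.22, with falsely significant excess mortality in about 3%, 7% and 10% of studies. If 25% or 50% of deaths are early (assumed), the ratio at R = 4 falls to 1.04 or 0.60. The two biases oppose each other, and the documents cannot say which is larger.

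**5. Severity stratification alone, still from time 0.** With 17.5% early deaths, the stratified log-rank test rejects in about 12 to 18% of null studies, almost all of them wrongly showing lower mortality in persisters. Stratification removes one bias and exposes the other.

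**6. Day-21 landmark.** Over the four scenarios in step 3, the unstratified log-rank test is falsely significant in about 10 to 32% of studies, and the severity-stratified test in about 5%. A repeat run of 3,000 studies per scenario agreed to within about two percentage points. A weaker imbalance matters less: 40% vs 25% with R = 2 gives a ratio of 1.40/1.25 = 1.12, and the repeat run put false significance near 7%.

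**The case against.** - **The definition fixes late status, not initial severity.** This stands. A patient with mild illness at diagnosis who relapses at day 30 is a persister; one who is hypoxemic at diagnosis and clears by day 20 is not. A reader might infer that the groups differ in initial severity by definition. Section 3.3 does not support that: only patients who never show symptoms or signs are barred from being persisters.
- **The protocol's rationale points partly the other way.** Section 2.1 says patients with impaired humoral immunity tend to have less acute toxicity but longer shedding. This stands as a reason not to assume a large imbalance. It does not show that severity at diagnosis is balanced between the groups.
- **ICU admission and hospital stay are in the Cox model and may absorb some severity.** This is partly right. The false-positive rates above are for log-rank tests; the bias left in the adjusted Cox model was not computed. But the log-rank test has no adjustment, and undated items that can follow persistence are not a reliable substitute.
- **Section 4.8 ends by saying that secondary endpoints will be described only for persisters, so mortality might not be compared at all.** That sentence conflicts with section 3.2, with the log-rank sample size in section 4.4.3 and with the Cox comparison in 4.8 itself. It needs reconciling, but it does not withdraw the planned comparison.

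**Conclusion.** The omission is certain: no listed covariate measures COVID-19 severity at time 0, and the definition and the mixed care settings make an imbalance likely. It should be corrected.

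The size of the bias is unknown. The 10 to 32% against about 5% rests on assumed severity shares, mortality ratios and 4% mortality, on a constant hazard, and on every persister being identified at day 21.

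Two stronger readings are tempting. A reader might infer that the plan will overstate mortality in persisters by a known amount. The documents give no severity data, and early deaths pull the other way, so neither size nor net direction is established. A reader might also infer that severity stratification is enough; step 5 shows that on its own it can leave the test misleading in the opposite direction. That two biases may partly cancel does not make the unadjusted result valid, and correcting only the timing would leave the severity bias exposed.

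**What to change.** In section 4.8:
- Add COVID-19 severity at time 0, as a short ordinal grade from clinical charts (for example no lung involvement, lung involvement, hypoxemia), and care setting at time 0 (inpatient or outpatient). Use both in the Cox and logistic models.
- Present the mortality log-rank test stratified by severity at time 0.
- Analyse persistence from a day-21 landmark or as a time-dependent exposure, and adopt this together with the severity adjustment. Because recurrence after day 21 also qualifies, a landmark analysis should use only status known at day 21; the time-dependent form can take in later qualifiers.
- State that hospital stay, ICU admission and superinfections are not measures of baseline severity.

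Cost: SAP wording and possibly one or two eCRF fields. The eCRF is not in the documents, so whether time-0 severity is already collected cannot be confirmed. Some time-0 imaging or oximetry will probably be missing for retrospective outpatients, and the plan should say how that is handled. At 4% mortality there are about 40 deaths, of which 40 × 0.825 = 33 fall after day 21 under a constant hazard. A three-level grade plus care setting adds three degrees of freedom to a list that already has 12 items, so the grade should stay coarse.
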